12.5.3 Secondary Endpoint

12.5.3.1 Secondary Efficacy Endpoint

For comparison of nabiximols treatment arm versus placebo treatment arm, if primary endpoint is significant, the statistical test will be performed on the secondary endpoint. The Type I error rate for comparing nabiximols treatment arm to placebo treatment arm for the secondary endpoint will be controlled at 0.05 level (2-sided) and inference will be provided. Otherwise, if primary endpoint does not reach the statistical significance at the nominal Type I error rate, nominal p-value for the secondary endpoint will be calculated but no claim could be made based on that p-value as per testing strategy described above.

The secondary endpoint change from baseline to D21 of each treatment period (as defined in [Section 10.2](#) and [Section 10.3](#)) in LLMT-4 (as defined in [Section 10.16](#)) will be analyzed in a similar way to the primary efficacy endpoint (see [Section 12.5.2.1](#)), during the 51-day randomized efficacy period using FAS. The comparison between nabiximols treatment arm and placebo treatment arm will be performed following the testing procedure outline just above and is assessing the secondary estimand (as defined in [Section 9.1](#)).

12.5.3.2 Sensitivity Analysis: Tipping Point

The primary efficacy analysis on secondary endpoint assumes data are either missing at random or missing not at random as per missing data handling strategy described in [Section 12.5.2.1.3](#).

To assess the robustness of the treatment effect with regard to missing data, sensitivity analyses based on a tipping point analysis will be performed for the secondary efficacy endpoint to assess the impact of the missing data assumed MNAR on the secondary estimand.

This analysis will impute missing nabiximols D21 data under a Missing Not at Random approach, using the FAS during the 51-day randomized efficacy period (see [Section 10.1](#)).

Thus, when no penalty is added the tipping point analysis is equivalent to the primary analysis of the secondary endpoint.

This analysis will be conducted using the same approach as the one described for primary efficacy endpoint (see [Section 12.5.2.2](#)). However, as LLMT-4 score is based on 4 muscle groups (and not 6 muscle groups as LLMT-6) as described in [Section 12.5.2.2](#), the Step 5 (Step 2 to Step 4 will be repeated for a plausible ^{nabiximols} value using a grid search method. Firstly larger changes in delta values (delta will range from 0 to 5 by increments of 5/4 where 5/4 represents the maximum effect of an individual MAS transformed score on LLMT-4) will be used. If the inference changes, then smaller changes in delta values (1/4 representing the change of 1 of LLMT-4 score) will be used to identify a more accurate tipping point between the last two delta values which were using larger changes (ie. last delta value with $p < 0.05$ and first delta value with $p \geq 0.05$).

The same tables, figures and listing as those performed for LLMT-6 (as described in [Section 12.5.2.3.3](#)) will be provided for LLMT-4.

12.5.4 Other Analyses based on MAS

12.5.4.1 Analysis based on LLMT-10

The **exploratory efficacy** analysis **associated with the LLMT-10 endpoint** is defined as the estimated mean treatment difference between nabiximols and placebo on the estimated change from baseline to D21 on the LLMT-10 score (as defined in [Section 10.16](#)) where MAS scores are collected during the 51-day randomized efficacy period, for all randomized patients belonging to the FAS. The comparison between nabiximols and placebo will be performed at a type I error level of 0.05 (two-sided) and nominal p-values will be provided. No adjustments for multiplicity will be made on that endpoint and no claim could be made based on that p-value as per testing procedure outline in [Section 12.5.1](#).

The same analyses as those conducted for LLMT-4 will be performed (see [Section 12.5.3.1](#)) apart from the tipping point analysis.

12.5.4.2 MI followed by Linear mixed-effect model with repeated measures for crossover data

Model Selection Before Multiple Imputations (MI)

The model will be selected before MI and all subsequent statistical analyses conducted on this model. The model selection process will NOT be reconducted for each imputed dataset.

The change from baseline to D21 of each treatment period (as defined in [Sections 10.2](#) and [10.3](#)) in LLMT-6, LLMT-4 and LLMT-10 scores (as defined in [Section 10.16](#)) will be analyzed using a linear mixed-effects model with repeated measures for crossover data using the SAS® GLIMMIX procedure with an identity link function and a normal distribution performed on each multiple imputed dataset. This model is an extension of the primary efficacy analysis by including the D1H3 post-dose timepoint.

The model will include period level LLMT-X* baseline covariate, period level treatment arm, treatment sequence, treatment period, visit, visit-by-period level LLMT-X* baseline covariate interaction and visit-by-period level treatment arm interaction as fixed effects. An unstructured covariance structure will be used to model the residual errors between LLMT-X* scores within the same patient across visit and period and the denominator degrees of freedom will be calculated according to the Kenward-Roger method (e.g. KR2, 2009 version). In case of non-convergence of the preferred model or memory space issues the compound symmetry (CS) covariance structure will be used. The final selected model from this process will be fitted to each of the 300 imputed datasets. Note: The model selection process will NOT be reconducted for each imputed dataset.

Pattern Mixture Model Placebo-based Multiple Imputation

Using the 300 imputed datasets obtained while performing primary analysis of LLMT-X* scores (see methodology in [Section 12.5.2.1.6](#)), each imputed dataset will be analyzed using a LME repeated measures for crossover data (described in [Section 12.5.4.2](#)). The result of each of these models will then be combined as described in [Section 12.5.2.1.7](#) to produce for each post-dose assessment (D1H3, D21), valid combined estimates for each treatment arm with corresponding SEs and 95% CIs as well as combined valid estimates of treatment difference in change from baseline in LLMT-X* with corresponding SEs, 95% CIs and nominal p-value for treatment arm comparison at D1H3 and D21.

Combined LS means change from period baseline and 95% CI will be plotted by timepoint per treatment arm.

Linear Mixed-effect Model with Repeated Measure for Crossover Data

The model fitted to the data will be the one selected in the 'Model Selection Before Multiple Imputations (MI) section above.

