12.5.2.1.6 Pattern Mixture Model Placebo-based Multiple Imputation Method

The Pattern mixture placebo-based multiple imputation method which is a “copy to reference method” will be implemented using baseline to predict D1H3 and D21 values in a MNAR model with indicator variables for treatment period, treatment sequence, and treatment.

For each of the 300 monotone by treatment period datasets generated as described in [Section 12.5.2.1.5](#), the remaining missing data will be imputed separately for each treatment period within each treatment arm using the REGRESSION method in conjunction with the MONOTONE statement and either MNAR or MAR statement (as described in [Table 12.5-1](#)) of the SAS® MI procedure.

- Step1, the imputation model will create 300 monotone by treatment period datasets, as described in [Section 12.5.2.1.5](#).
- Step 2a applied to Period 1 scores,
 - For patients on placebo treatment arm (i.e. placebo/nabiximols treatment sequence) and/or due to COVID-19 with non-missing LLMT-6 baseline score, LLMT-6 scores will be imputed sequentially at each post period baseline assessment (D1H3, D21) using a MAR imputation based on all non-missing LLMT-6 scores. Therefore, the models used to generate each post period baseline LLMT-6 scores are:
 - placebo LLMT-6 Period 1 D1H3 = placebo LLMT-6 Period 1 baseline score.
 - placebo LLMT-6 Period 1 D21 = placebo LLMT-6 Period 1 baseline score and placebo Period 1 D1H3 LLMT-6 score.
 - For patients on nabiximols treatment arm (i.e. nabiximols/placebo treatment sequence) with non-missing LLMT-6 baseline score, LLMT-6 scores will be imputed sequentially at each post period baseline assessment (D1H3, D21) using a MNAR imputation based on all non-missing LLMT-6 scores. Therefore, the models used to generate each post period baseline LLMT-6 scores are:

- nabiximols LLMT-6 Period 1 D1H3 = placebo LLMT-6 Period 1 baseline score.
- nabiximols LLMT-6 Period 1 D21 = placebo LLMT-6 Period 1 baseline score and placebo Period 1 D1H3 LLMT-6 score.
- Step 2b applied to Period 2 scores,
 - For patients on nabiximols treatment arm (i.e. placebo/nabiximols treatment sequence) and/or due to COVID-19 with non-missing LLMT-6 baseline score, LLMT-6 scores will be imputed sequentially at each post period baseline assessment (D1H3, D21) using a MAR imputation based on all non-missing LLMT-6 scores. Therefore, the models used to generate each post period baseline LLMT-6 scores are:

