12.5.2.1.8 Linear Mixed-effects Model for Crossover Data

The primary analysis model will be selected before multiple imputation and all subsequent statistical analysis conducted on this final model. The final selected model (after convergency and residual diagnostics and outlier searches, see below) will be fitted to each of the 300 imputed datasets. The model selection process will NOT be reconducted for each imputed dataset.

The change from baseline to D21 of each treatment period (as defined in [Section 10.2](#) and [Section 10.3](#)) in LLMT-6 (as defined in [Section 10.16](#)) will be analyzed with a LME model for crossover data using the SAS® GLIMMIX procedure with an identity link function and a normal distribution. The change from period level baseline to D21 in LLMT-6 score will be included as the dependent variable. Hence, each patient will contribute two measurements to the model, one for each period of the study.

The preferred model will include a period level LLMT-6 baseline (pre-dose measurement) covariate, period level treatment arm, treatment period, and treatment sequence as fixed effects). An unstructured (UN) covariance structure will be used for the repeated LLMT-6 measurements of the changes from baseline in each treatment period and the denominator degrees of freedom will be calculated according to the Kenward-Roger method (e.g., KR2, 2009 version)

In case of non-convergence of the preferred model or memory space issue, the compound symmetry covariance structure will be applied to the preferred model described above.

This model will provide the least squares mean estimates for each treatment arm, along with the SEs and 95% CIs as well as, the least squares mean (LS mean) estimate of the mean treatment difference between nabiximols and placebo in change from baseline in LLMT-6 along with SE of the difference, 95% CI and associated nominal p-values will be presented.

In addition, this model will present the LSmeans estimates along with 95% CIs for each treatment period and treatment sequence, as well as the difference between treatment periods and treatment sequences and associated nominal p-values.

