12.5.2.3 Supplementary Analyses Based on LLMT-6

12.5.2.3.1 Subgroup Analysis for Primary Endpoint

The treatment effect across the different subgroups indicated in Table 12.5-2 will be explored on the primary efficacy endpoint: LLMT-6.

Table 12.5-2 Subgroup Analyses of Primary Efficacy Endpoint

Group variables	Subgroup	Comments
Sex	Male Female	
Prior cannabis use	Yes No	
Baseline LLMT-6 category (cut off=2)	Period 1 baseline LLMT-6 <= 2 Period 1 baseline LLMT-6 > 2	Baseline LLMT-6 categories refers to period 1 baseline score
Baseline LLMT-6 category (cut off=3)*	Period 1 baseline LLMT-6 <= 3 Period 1 baseline LLMT-6 > 3	

If the value of a group variable cannot be determined, the patient will be excluded from the corresponding subgroup analysis.

The treatment arm-by-subgroup interaction will be assessed for the primary efficacy endpoint using the 300 imputation datasets derived to perform the primary efficacy analysis as described in [Section 12.5.2.1.6](#). Each imputed dataset will be analysed using linear mixed-effects model for crossover data as described in [Section 12.5.2.1.8](#) with subgroup and subgroup-by-period level treatment arm interaction, as 2 additional fixed effects. Result from each linear mixed-effects model for crossover data will then be combined as described in [Section 12.5.2.1.7](#).

For each subgroup analyses, the following estimates will be presented. Within each subgroup; (i) the combined adjusted LS mean (SEs and 95% CIs) of the change from period baseline to D21 for nabiximols and placebo will be presented, (ii) the combined difference in LS means (nabiximols–placebo) together with SEs and 95% CIs as well as the nominal p-value will be presented. The subgroup-by-treatment arm interaction nominal p-value will be presented. In addition, frequency count and descriptive statistics for each subgroup will be presented in a separate table. Forest plots will be used to present subgroup analyses results. The forest plot created from subgroup analyses will display number of patients, all combined estimates (i, ii), including combined 95% CI for (ii) and interaction p-values.

If, in each treatment arm by subgroup, the number of patients is less than 5, only summary statistics will be displayed and no subgroup analyses will be conducted.

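### The repeated-measures model in SAP 12.5.4.2 has no visit-by-period term, so it forces one period effect on D1H3 and D21; this matters only if the true period effect differs between the two visits

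*SAP*

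**What the plan says.** SAP 12.5.4.2 describes its model for LLMT-6, LLMT-4 and LLMT-10 as follows: "This model is an extension of the primary efficacy analysis by including the D1H3 post-dose timepoint". After the period-level baseline and treatment arm, the fixed effects are "treatment sequence, treatment period, visit, visit-by-period level LLMT-X* baseline covariate interaction and visit-by-period level treatment arm interaction as fixed effects". No visit-by-period or visit-by-sequence term is listed, and the entries for this analysis in Appendix 14 add none.

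On covariance: "An unstructured covariance structure will be used to model the residual errors between LLMT-X* scores within the same patient across visit and period". Compound symmetry is the fallback. The output includes a "nominal p-value for treatment arm comparison at D1H3 and D21", with estimates, SEs and 95% CIs at both visits.

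The primary model (SAP 12.5.2.1.8) uses the D21 change only, one value per period. Besides the baseline covariate it has "period level treatment arm, treatment period, and treatment sequence as fixed effects". Its period effect is therefore specific to D21.

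The imputation that feeds both models (SAP 12.5.2.1.6) is specific to the period: "the remaining missing data will be imputed separately for each treatment period within each treatment arm".

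**The concern.** D1H3 is the change over about three hours after a single spray on the first day of a period. D21 is the change over three weeks of titration and maintenance. Nothing in the documents says that a Period 2 versus Period 1 shift should be the same for both, yet a single period coefficient imposes this.

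If the two shifts differ, the fitted common effect is wrong at one or both visits. The misfit enters the residual covariance and inflates the model SEs. If the sequences are unequal in size, part of it also enters the treatment estimates. The D21 result could then differ from the primary result partly because of an unstated constraint, although the model is presented as an extension of the primary analysis. The D1H3 contrast could move for the same reason. The analysis model is also more restrictive than the imputation model behind it.

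**Working it through.** **1. Reading of the terms.** The wording of the visit-by-treatment term in 12.5.4.2 could be taken to include visit-by-period. It does not. In 12.5.2.1.8, *period level treatment arm* names the treatment factor, and treatment period is listed separately. The subgroup model in 12.5.2.3.1 uses the phrase in the same way: "subgroup and subgroup-by-period level treatment arm interaction, as 2 additional fixed effects".

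**2. The plan's own figures (SAP 8.2).** Inputs: difference -0.30, SD of paired differences 0.71, two-sided 5%, 80% power.
- Normal approximation: ((1.960 + 0.842) × 0.71 / 0.30)² = 43.96. The paired t-test with the noncentral t gives 46 (power 80.07%), as stated.
- 46 / 0.90 = 51.1, so 52, as stated.
- Power at 68 completers with SD 0.71 is 93.0%, which agrees with the stated figure of above 90%.
- The simple SE at N = 68 is 0.71 / √68 = 0.086. The simulation below gives 0.0853 at D21 with the term included.

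**3. Source of the bias.** Let the true period effect at visit v exceed the fitted common effect by m(v). Within-patient differences (nabiximols minus placebo) carry -m(v) in the nabiximols/placebo sequence (n1 patients) and +m(v) in the other (n2). Averaged over patients:

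bias(v) = m(v) × (n2 - n1) / N

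This is zero when n1 = n2. Write the gap as the period effect at D21 minus that at D1H3. Then m(D21) - m(D1H3) = gap, so the two biases differ by gap × (n2 - n1) / N. The covariance decides only how this total is divided between the visits.

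**4. Simulation.** 2×2 crossover, N = 68, two visits per period, period-level baseline, complete data, unstructured 4×4 covariance, fitted with and without visit-by-period. The following are assumed, because the documents give no values: gap 0 to 0.8, D1H3 paired-difference SD 0.5, between-visit correlation 0.4, between-period correlation 0.3.

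Equal sequences (34/34), no bias at any gap:

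| Gap | D21 SE without term | D21 change | D1H3 SE without term | D1H3 change |
|---|---|---|---|---|
| 0 | 0.085 | none | 0.060 | none |
| 0.2 | 0.0873 | +2% | 0.0603 | +0.5% |
| 0.4 | 0.0930 | +9% | 0.0611 | +2% |
| 0.8 | not tabulated | +32% | not tabulated | +7% |

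The reference SEs with the term are 0.0853 (D21) and 0.0600 (D1H3). The empirical spread of the estimates hardly changes, so the intervals are too wide. D21 coverage at gap 0.4 is 96.6% without the term and 95.3% with it.

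Unequal sequences (n1/n2), shift in the treatment estimate:

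| n1/n2 | Gap | D21 | D1H3 | Distance between shifts | Formula |
|---|---|---|---|---|---|
| 36/32 | 0.2 | -0.009 | +0.003 | 0.012 | 0.2 × 4/68 = 0.012 |
| 36/32 | 0.4 | -0.018 | +0.005 | 0.023 | 0.4 × 4/68 = 0.024 |
| 38/30 | 0.4 | -0.036 | +0.011 | 0.047 | 0.4 × 8/68 = 0.047 |

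Signs reverse if the placebo-first sequence is the larger or if the gap is negative. At gap 0 the estimates with and without the term agree.

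**5. Sensitivity to the covariance.** D1H3 SD was varied from 0.35 to 0.71, between-visit correlation from 0.1 to 0.8, and between-period correlation up to 0.6. At gap 0.2 the D21 SE rises 1.0% to 5.5% and the D1H3 SE 0.1% to 1.1%. At 36/32 the D21 shift is 0.006 to 0.014 in size and the D1H3 shift 0.001 to 0.006. With between-visit correlation 0.8, the small D1H3 shift (-0.002) has the same sign as the D21 shift, so the opposite direction holds for the main assumptions and not for every covariance.

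**The case against.** The strongest reply is that the harm is conditional and small. Without a difference in period effect between visits there is none, and the documents neither show nor size such a difference. Gaps of 0.3 or more equal or exceed the whole target effect of 0.30. At gap 0.2 and 36/32, the D21 shift is about a tenth of an SE (0.009 / 0.0853). With equal sequences the error is conservative. Allocation is 1:1, and the FAS keeps every randomized and dosed patient, so dropout does not unbalance the FAS analysis. All of this stands.

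Some safeguards also exist. SAP 12.5.2.1.9 reports the primary model's period effect, and 12.5.2.3.3 summarizes LLMT-6 by arm, period and time point. A visit-dependent period shift would be visible there, but these outputs do not correct the model.

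Two stronger readings are tempting. A reader might infer that the omission by itself widens intervals and biases both visits; the equal-period-effect case shows that it does not. A reader might also infer that the trial's main conclusion is at risk. The documents do not support that: the primary and key secondary models fit the D21 period effect freely, and the repeated-measures analysis is supplementary or exploratory, with nominal p-values outside the testing hierarchy.

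The objection leaves one thing unanswered: the SAP gives no reason for the constraint, in a model offered as an extension of one that lacks it.

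**Conclusion.** The specification gap is real and minor. The model in 12.5.4.2 imposes equal period effects at D1H3 and D21. If they differ, D21 model SEs are about 2% to 9% too large for gaps of 0.2 to 0.4 with equal sequences, with conservative coverage and no bias. Unequal sequences add a shift of about -0.01 to -0.02 at D21 for 36/32, and -0.036 for 38/30 at gap 0.4, against a target effect of -0.30. If the period effects are equal there is no harm.

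These sizes rest on the assumed gaps, variances and correlations above, on N = 68 and on complete data; imputation and the compound symmetry fallback were not simulated. The results concerned are the repeated-measures analyses of LLMT-6, LLMT-4 and LLMT-10 and the LLMT-6 time-window analysis in 12.5.4.3.3. That last analysis may use the Per Protocol set, where sequence balance is less assured.

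A disagreement with the primary result at D21 should not be put down to this constraint alone, because sequence, too, has only a main effect in this model.

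**What to change.** Before unblinding, add a *visit-by-treatment period interaction* to the fixed effects in SAP 12.5.4.2. Section 12.5.4.3.3 refers to that model, so the change carries over. If D21 is meant to have the same mean structure as the primary model, also add a *visit-by-treatment sequence interaction*; the period term alone does not achieve this.

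The cost is 1 df per term. When the period effects are equal, the simulated cost of the period term is nil at 34/34. It is visible only with clear imbalance: D21 SE 0.0878 against 0.0865 at 42/26 (0.0878 / 0.0865 = 1.015). The cost of the sequence term was not simulated. With the period term included, the shifts disappear and, at 34/34, the SEs return to 0.085 at D21 and 0.060 at D1H3 for every gap examined.

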12.5.4.3 Impact of Intercurrent Events

12.5.4.3.1 Impact of Missing individual transformed MAS muscle score

To assess the robustness of LLMT-6, LLMT-4 and LLMT-10 scores to missing individual muscle scores, the change from baseline to D21 of each treatment period (as defined in [Section 10.2](#) and [Section 10.3](#)) for LLMT-6, LLMT-4 and LLMT-10 scores will be analyzed using the same approach as the one described respectively in [Section 12.5.2.1](#) in [Section 12.5.3.1](#)**Error! Reference source not found.** and in [Section 12.5.4.1](#) (LME model for crossover data applied to MI imputed datasets). The analyses will be conducted on FAS during the 51-days randomized period but only using LLMT-6, LLMT-4 and LLMT-10 scores derived without any missing individual MAS transformed muscle score.

12.5.4.3.2 Impact of Study/Treatment Discontinuation

To assess the robustness of the MAS scores results with regard to permanent premature treatment discontinuation and/or study withdrawal, the change from baseline to D21 of each treatment period (as defined in [Section 10.2](#) and [Section 10.3](#)) for LLMT-6, LLMT-4 and LLMT-10 scores will be analyzed by means of a linear mixed-effects model for crossover data applied on MI datasets using the approach described respectively in [Section 12.5.2.1](#), [Section 12.5.3.1](#) and in [Section 12.5.4.1](#) but conducted:

- during the 51-day on-treatment efficacy period (as defined in [Section 10.1](#)) using only on-treatment assessments (assessments obtained post treatment discontinuation are excluded from the analysis),

- during the 51-day randomized period using the Study Completer Analysis Set.

